8. STUDY ASSESSMENTS/VISITS

8.1 Study visits:

The study comprises three visits: Visit 1 (baseline), Visit 2 (3rd month), and Visit 3 (6th month).

8.2 Study assessments:

At each visit, the following examinations will be performed in both eyes in the following order:

- OSDI questionnaire
- NIBUT
- Schirmer test
- TBUT
- Corneal staining evaluation (Oxford scale)

All above mentioned examinations and all evaluations required by the study are part of the normal clinical practice.

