4. STUDY DESIGN

4.1 Study Description

This spontaneous, prospective, non-randomized, parallel-group, phase IV study was conducted in compliance with the tenets of the Declaration of Helsinki.

All study participants were fully consented, and written informed consent was obtained.

This study included patients with refractory MGD. Refractory MGD is defined as symptomatic MGD (OSDI > 13 points) despite 2 months of first-line treatment with lacrimal substitutes 3 times per day and meibomian gland expression with warm compresses twice per day.

The study will consist of 3 visits: Visit 1(Baseline - day 0), Visit 2 (day 90 ± 5 - 3rd month), Visit 3 (day 180 ± 5 - 6 month). At each visit, patients will receive an OSDI questionnaire, NIBUT, type I Schirmer test and AS assessment, including TBUT, corneal staining (Oxford scale)

At baseline, eligible patients will be enrolled and treated with the assigned protocol. The investigators will assign the protocol (non-randomized) in a 1:1 ratio.

At Visit 2, NIBUT, TBUT, Oxford scale and OSDI improvement will be evaluated compared with Visit 1. Patients will be carefully asked about their compliance with the treatment. Patients who interrupted the treatment for adverse events or low compliance (<75% of the protocol adherence) will exit the study and be excluded from the analysis.

At Visit 3, the study population will be evaluated as done in Visit 2

The protocols in the study are the following:

- LCD (low-dose continuous protocol) - 50 mg of doxycycline for three months
- FPP (Full-dose pulsed protocol) - 100 mg of doxycycline for the first 15 days of the month for three months.

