5.2 Secondary endpoints

The study's secondary endpoints are the Low- and high-tech anterior segment parameters (NIBUT, TBUT, Oxford class).

For these parameters, the changes occurring in the two groups at each visit compared to baseline will also be evaluated.

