6.2 Inclusion criteria

- 18 years or older
- provided written informed consent
- OSDI score of 13 or more at the baseline visit after at least two months of first-line therapy (artificial tears and warm compresses)
- Clinical diagnosis of MGD
- Type 1 Schirmer test > 10 mm
- No previous history of allergy or sensitivity to doxycycline,
- No use of additional topical or systemic antibiotics for the prior 2 months
- No use of topical anti-inflammatory agents (ex: corticosteroids or cyclosporine) for the prior 3 months.

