11.2 Sample size

The sample size estimate was based on a test for before-after studies using a paired t-test, defining a 1-sec change in Break-Up Time as clinically relevant and a standard deviation of 2.3 sec. Setting the error to 2.5% (one-tailed), 43 patients would be required, assuming a power of 80%. Assuming drop out, the final enrollment will be 65 patients.

Clinical Trial Protocol CPDOXY1

Comparison between continuous and pulsed oral doxycycline treatment protocols for refractory meibomian gland dysfunction - 9 months follow-up prospective study

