11.3 Statistical analysis

11.3.1 Efficacy analysis

Treatment and analysis will be performed on the worst of the two eyes at diagnosis. Worst eye will be defined based on TBUT or, in case of identical TBUT between the two eyes, OXFORD class. In case of identical TBUT and OXFORD class, NIBUT will be considered.

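### The prescribed order places the Schirmer strip before TBUT and Oxford staining, which adds avoidable noise to two secondary signs and to the choice of study eye (minor)

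*Protocol*

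**What the plan says.** Section 8.2 of the protocol prescribes a sequence: "At each visit, the following examinations will be performed in both eyes in the following order". The list that follows is OSDI, NIBUT, Schirmer, TBUT, corneal staining on the Oxford scale.

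Section 4.1 lists the tests in the same sequence and names the Schirmer variant: "At each visit, patients will receive an OSDI questionnaire, NIBUT, type I Schirmer test and AS assessment, including TBUT, corneal staining (Oxford scale").

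Three other places determine what the order affects:

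- Section 5.2: "The study's secondary endpoints are the Low- and high-tech anterior segment parameters (NIBUT, TBUT, Oxford class").
- Section 11.3.1: "Worst eye will be defined based on TBUT or, in case of identical TBUT between the two eyes, OXFORD class". NIBUT is the last tie-break.
- Section 6.2, the only use that the protocol makes of the Schirmer result: "Type 1 Schirmer test > 10 mm".

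Neither section 8.2 nor section 4.1 states a waiting time, a separate session or any other separation between the strip and the readings after it. The visit table in section 14.7 names neither Schirmer nor corneal staining and does not alter the order.

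**The concern.** A type I Schirmer strip rests on the lid margin, touches the ocular surface, soaks up tears and stimulates reflex tearing. TBUT is meant to describe the stability of the tear film, and Oxford staining the state of the surface epithelium. Those are the properties that the strip can disturb. This is general measurement reasoning; the protocol does not discuss it.

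The list starts with the least invasive steps, a questionnaire and then a non-invasive break-up time. It then puts the strip ahead of the two remaining signs. A site that follows section 8.2 to the letter reads NIBUT before the strip and TBUT after it, so the two break-up times of one eye are not taken under the same conditions.

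At stake are the validity and precision of TBUT and Oxford grade as secondary endpoints, and the reliability of the rule that decides which eye supplies the signs for analysis.

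**Working it through.** The protocol contains no figure for the effect of the strip, so there is no number to reproduce. The check sets the sections side by side.

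**Step 1. Position and role of each test**

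| Position in 8.2 | Test | Relation to strip | Role in the plan |
|---|---|---|---|
| 1 | OSDI | before | both primary endpoints (5.1) |
| 2 | NIBUT | before | secondary endpoint (5.2); last tie-break for study eye (11.3.1) |
| 3 | Schirmer, type I | – | entry criterion (6.2); not an endpoint in 5.1 or 5.2 |
| 4 | TBUT | after, next in the list | secondary endpoint (5.2); first criterion for study eye (11.3.1) |
| 5 | Oxford staining | after, with TBUT in between | secondary endpoint (5.2); first tie-break for study eye (11.3.1) |

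Two of the three secondary signs follow the strip. So do the first two of the three criteria for the study eye. Nothing before the strip is affected by it at that visit.

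**Step 2. What a disturbance would do to a change from baseline**

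Write a reading after the strip as the true value plus a constant shift c plus a random error e. The change from baseline is then

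(true follow-up + c + e₁) − (true baseline + c + e₀) = true change + (e₁ − e₀).

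The constant shift cancels, because section 8.2 uses the same order at every visit. The random part does not. If the two errors are independent with variance s², it adds 2s² to the variance of the change. The documents give no value for s. The cancellation also assumes an additive shift that does not depend on the state of the eye, which is less secure for a graded scale such as Oxford.

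**Step 3. What it would do between the arms**

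The order is the same in both arms. Under the same assumptions the disturbance makes the comparison noisier and does not push it toward either protocol.

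**Step 4. What it would do to eye selection**

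The study eye is chosen on the difference in TBUT between the eyes. After the strip that difference carries the errors of both eyes, so when the eyes are close the noise can change which one is called worse. OSDI is a patient-level questionnaire, so this reaches only the signs.

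**Step 5. Is there a safeguard elsewhere?**

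None was found in sections 4.1, 8.2, 11.3.1 or 14.7. Section 8.2 says that all examinations belong to normal practice. That explains why they are done, not why they are done in this sequence.

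**The case against.** **The harm is not documented.** No section says that the strip alters TBUT or staining, and section 8.2 fixes a sequence, not the time between tests. A site manual could set a pause. This stands as a limit: the mechanism is plausible, its size is unknown, and it cannot be said that the readings are taken straight after the strip. It does not remove the point, because the protocol itself prescribes the less favourable order and states no pause.

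**The effect is the same in both arms and misses the primary endpoints.** This stands, and it is the main reason for the low severity.

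**The power of the trial.** A reader might infer that the sample size in section 11.2 is undermined. The documents do not support that:

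- The section sizes the study by "defining a 1-sec change in Break-Up Time as clinically relevant and a standard deviation of 2.3 sec". It does not say whether this is TBUT or NIBUT, and NIBUT is read before the strip.
- It gives no source for the standard deviation, which may already include readings taken in this order.
- The calculation is for a before-after test with 43 patients, while 65 are to be enrolled and the objectives compare the two arms.

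Any power figure would rest on invented error sizes.

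**Bias between arms.** A reader might also suspect that the strip favours one arm. Nothing in the protocol shows this.

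**The remedy has its own interference.** With Schirmer last, the eligibility test follows the dye that TBUT and staining are assumed to use. That is true. It moves any disturbance to a single entry threshold and away from two endpoints and the choice of eye.

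**The schedule is inconsistent.** Sections 4.1 and 8.2 place Schirmer at each visit, while section 14.7 does not list it at all. Whether the strip precedes the follow-up readings is therefore not fully settled. The two sections with explicit wording say that it does.

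**Conclusion.** The point holds as a minor one. As written, the protocol has TBUT and Oxford staining read after a contact test that serves only eligibility, at every visit and with no stated safeguard. The expected consequence is additional noise, alike in both arms, and reduced validity in two of the three secondary signs and in the selection of the study eye.

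The size cannot be given from the documents. The conclusion rests on two assumptions: that the strip disturbs the tear film and surface to some degree, and that the disturbance has not passed when TBUT and staining are read. It does not extend to OSDI, to the NIBUT readings, to a bias between the arms or to the adequacy of the sample size.

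**What to change.** Reorder section 8.2, and the list in section 4.1, to: OSDI, NIBUT, TBUT, corneal staining (Oxford), then Schirmer last at any visit where it is done.

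State in section 14.7 at which visits Schirmer and staining are performed, so that the table agrees with sections 4.1 and 8.2. Schirmer could be limited to Visit 1, since no endpoint uses it later, but only together with the new order. Dropping it at Visits 2 and 3 while leaving it ahead of TBUT at baseline would put baseline readings after the strip and follow-up readings without one, and the constant shift in the working would no longer cancel. For the same reason, any patient already examined in the present order at baseline should keep that order at follow-up.

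The cost is a one-line change, with no added test, visit or staff. The downside is that the eligibility Schirmer follows fluorescein instillation. If Schirmer is limited to Visit 1, a descriptive follow-up value is lost.

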9. PATIENT, STUDY, AND SITE DISCONTINUATION

9.1 End of treatment

In this prospective study, study treatments will end after three months after the last enrollment.

9.2 End of the study

Enrollment will end as soon as the target number of patients is achieved. The study will end six months after the last patient's enrollment.

10. SAFETY AND ADVERSE EVENTS

10.1 Safety evaluation

Clinical Trial Protocol CPDOXY1

Comparison between continuous and pulsed oral doxycycline treatment protocols for refractory meibomian gland dysfunction - 9 months follow-up prospective study

During the treatment period (from V1 to V2), patients can contact any member of the study medical staff with doubts or suspected adverse events. The investigators will determine if a drug-related adverse event (AEs) has occurred.

AEs will be coded according to the most current Medical Dictionary for Regulatory Activities (MedDRA) classification.

The investigator will record the nature, severity, treatment and outcome of the AE, and will determine their association with the investigational products or procedures involved in the clinical study.

10.2 Adverse event: Definitions

An AE is any untoward medical occurrence associated with the use of a device in humans without any judgment about relationship.

This includes events related to the investigational device or the vehicle. The investigator will determine and record the seriousness, severity, relationship, and outcome for all AEs

10.3 Causality Assessment

The investigator or designee is responsible for assessing the relationship between AEs and the study drug. Additionally, the investigator or designee is responsible for providing appropriate treatment for the event and for adequately following the event until resolution. The clinical investigator or responsible designee should determine the study device relationship using the following explanations:

Certain Event or laboratory test abnormalities, with plausible time relationship to medical drug use, cannot be explained by disease or other interventions. The response to withdrawal is plausible and rechallenge satisfactory, if necessary.

Probable / Likely Event or laboratory test abnormality, with reasonable time relationship to medical device use and unlikely to be attributed to disease or other interventions. Response to withdrawal is clinically reasonable. Re-challenge not required.

Possible Event or laboratory test abnormality, with reasonable time relationship to medical device use and that could also be explained by disease or other interventions.

Information on withdrawal may be lacking or unclear.

Unlikely Event or laboratory test abnormality with a time to medical device use that makes a relationship improbable (but not impossible). Disease or other interventions provide plausible explanations.

Unrelated; A clinical event that appears before using the medical device or can be fully explained by other factors.

Conditional/Unclassified Event or laboratory test abnormality; more data for proper assessment needed or additional data under examination.

Unclassifiable; Report suggesting an adverse reaction that cannot be judged because information is insufficient or contradictory. Data cannot be supplemented or verified.

10.4 Severity Assessment

Clinical Trial Protocol CPDOXY1

Comparison between continuous and pulsed oral doxycycline treatment protocols for refractory meibomian gland dysfunction - 9 months follow-up prospective study

The intensity (severity) of an AE is assessed by the Investigator and graded as mild, moderate or severe, irrespective of the relationship to the device or the seriousness of the event.

Mild - Discomfort noticed, but no disruption to daily activity

Moderate - Discomfort sufficient to reduce or affect normal daily activity

Severe - Inability to work or perform normal daily activity

10.5 Outcome Assessment

The outcome assessment for an AE will be defined as follows:

- resolved
- resolved with sequelae
- ongoing
- death
- unknown

10.6 Serious Adverse Event (SAE)

An AE is considered “serious” if, it results in any of the following:

- death
- a life-threatening illness or injury, or
- a permanent impairment of a body structure or a body function, or
- required in-patient hospitalization or prolongation of existing hospitalization, or
- medical or surgical intervention to prevent life-threatening illness, injury or permanent impairment to a body structure or a body function, or
- led to fetal distress, fetal death or a congenital abnormality or birth defect.

This includes adverse AEs that might have led to an SAE if a) suitable action had not been taken or b) intervention had not been made, or c) if circumstances had been less fortunate. A planned hospitalization for a pre-existing condition, or a procedure required by the protocol, without a serious deterioration in health, is not considered to be a serious AE.

10.7 Drug Deficiency

The investigational device's inadequacy is related to its quality, safety, or performance, such as malfunction, misuse, user error, and inadequate packaging or labelling.

10.8 Adverse Device Effect

ADVERSE EVENT RELATED TO THE USE OF AN INVESTIGATIONAL MEDICAL DEVICE.

This includes any AE resulting from insufficiencies or inadequacies in the instructions for use or any malfunction of the investigational medical device. This also includes any event that is a result of a use error or intentional misuse.

UNANTICIPATED SERIOUS ADVERSE DEVICE EFFECT (USADE)

Unanticipated Serious Adverse Device Effect (USADE) is a serious adverse device effect, which by its nature, incidence, severity or outcome has not been previously identified)

Clinical Trial Protocol CPDOXY1

Comparison between continuous and pulsed oral doxycycline treatment protocols for refractory meibomian gland dysfunction - 9 months follow-up prospective study

10.9 Collection of Adverse Events (AE)

Any AE occurring prior to signing the ICF should be considered medical history or a preexisting condition will be collected on the Medical History eCRF.

All AEs will be collected from the signing of the ICF through the 3-year follow-up and entered into the AE section of the eCRF. Serious AEs will be collected from the signing of the ICF through the 36-month follow-up and recorded on the AE eCRF. SAEs will also be reported within 24 hours using the Serious Adverse Event Report Form.

At V2, the investigator will determine whether any AE has occurred after carefully interrogating the patient. The investigator will also determine and record the seriousness, severity, relationship, and outcome for all AEs.

10.10 Device Deficiencies

Information will be collected on investigational medical device deficiencies from the investigators. An investigation of the medical device deficiency is performed promptly to determine the root cause of the deficiency. Device deficiencies will be recorded in the eCRF, and will also be reported using the SAE Form (even if any device deficiency does not result in an AE).

10.11 Reporting of Adverse Events and/or Device Deficiency

All AEs, SAEs and device deficiencies will be reported to the regulatory authorities and IECs in accordance with the current country specific regulatory and IRB/IEC requirements.

11. STATISTICAL CONSIDERATION AND ANALYTICAL PLAN

11.1 Definition of study populations

11.1.1 All Patients Analysis Set

This analysis is not ideal for this study. It will be performed as a secondary analysis, but publication will be based on ITT analysis.

11.1.2 Intent-to-Treat (ITT) Analysis Set

Signs and symptoms will be analyzed using an intent-to-treat approach. In case of missing data, the last observation available will be carried forward. This will be the primary analysis.

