1.2 Current therapeutic options

The patient should understand that a complete cure is usually not possible for blepharitis. As a matter of fact, the main goal of the treatment is the control of the ocular symptoms in the majority of the cases. The main treatments for MGD are:

- Warm compresses
- Eyelid cleansing and massage to express the meibomian glands
- Antibiotics (topical and/or systemic)
- Topical anti-inflammatory agents (e.g., corticosteroids, cyclosporine)

These treatment options are often used in combination. The optimal treatment regimen often requires persistence and a trial-and-error approach.

An initial step in treating MGD patients is to recommend warm compresses and eyelid cleansing with the addition of ocular lubricants. For patients with MGD, whose chronic symptoms and signs are not adequately controlled with the previous approach, oral tetracyclines and topical antibiotics may be helpful. Doxycycline, minocycline, or tetracycline can be given daily and tapered after clinical improvement is noted. Alternatively, oral erythromycin or azithromycin can be used, especially in women of childbearing age and children. [1-2]

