3. STUDY OBJECTIVES

3.1 Primary objective

To evaluate which of the protocols in the study (LCD Vs FPP) has the greatest impact on refractory MGD patient's symptoms (OSDI) on a six-month follow-up

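### Carry-forward in the primary analysis enters month-3 OSDI as the month-6 off-drug outcome for patients missing at Visit 3, and the resulting error in the arm comparison can have either sign

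*Protocol*

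**What the plan says.** Section 11.1.2 sets an intent-to-treat approach for signs and symptoms and adds: "In case of missing data, the last observation available will be carried forward". It then states "This will be the primary analysis", and section 11.1.1 says publication will rest on it.

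The primary objective (section 3.1) asks which regimen "has the greatest impact on refractory MGD patient's symptoms (OSDI) on a six-month follow-up". Sections 4.1 and 8.1 schedule three visits: baseline, month 3 and month 6. Both regimens last three months (sections 4.1 and 7.3), and section 10.1 describes the treatment period as ending at Visit 2 ("During the treatment period (from V1 to V2"). The interval from Visit 2 to Visit 3 is thus planned to be off drug.

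Two other statements bear on the rule. Section 1.2 says of the disease: "The patient should understand that a complete cure is usually not possible for blepharitis". Section 4.1 has patients who stop for adverse events, or whose adherence is under 75%, leave the study at Visit 2 and be left out of the analysis. That conflicts with the intent-to-treat rule in section 11.1.2.

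**The concern.** Month 6 adds one thing to month 3: whether the benefit lasts once the drug has stopped. Where Visit 3 is missing, carry-forward assumes that it does. The only post-baseline value available to carry is the one from Visit 2.

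That value also means different things in the two arms. In the continuous arm (LCD) it is taken at the end of treatment. In the pulsed arm (FPP) the last 15-day pulse ends at about day 75, so it is taken about two weeks after the last dose.

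The responder endpoint has the same weakness: a patient with more than 7 points of improvement at Visit 2 who misses Visit 3 stays a month-6 responder. A patient lost before Visit 2 has the baseline carried forward and is scored as no change. The month-6 result then mixes off-drug values, month-3 values and baselines, in proportions set by the timing of drop-out in each arm. The paired t-test in section 11.3.1.1 takes the within-arm error directly. The comparison in the primary objective, and the chi-square test if used to compare arms, take the difference between arms.

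**Working it through.** **The plan's own figure.** Section 11.2 gives 43 patients for a paired t-test with a 1-sec change, SD 2.3 sec, one-tailed 2.5% and 80% power.

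- Normal approximation: ((1.960 + 0.842) × 2.3 / 1)² = 41.5, so 42.
- With the t correction: 41.5 + 1.960²/2 = 43.4.
- Exact noncentral t: power 0.795 at n = 43 and 0.805 at n = 44.

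The 43 is reproduced to within one patient. The section continues: "Assuming drop out, the final enrollment will be 65 patients". No rate is given. The implied allowance is (65 − 43)/65 = 22/65 = 33.8%.

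**Timing of the carried value.** Taking 30-day months, the third FPP pulse runs from day 60 to day 75. Visit 2 is at day 90 ± 5, which is 10 to 20 days later. For LCD, day 90 is the end of treatment.

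**Error within one arm.** Let q be the fraction seen at Visit 2 but missing at Visit 3, e the fraction lost before Visit 2, D the mean month-3 improvement and r the mean worsening from month 3 to month 6. If those lost would have followed the same mean course as the others,

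error in month-6 improvement = q × r − e × (D − r).

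The first term overstates and the second understates. The protocol gives none of q, e, D or r by arm, so the values below are assumptions.

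- Upper case, all implied loss after Visit 2 (q = 0.338, e = 0): 0.338 × 3 = 1.0, 0.338 × 7 = 2.4 and 0.338 × 10 = 3.4 OSDI points.
- Early loss (e = 0.10, q = 0, D = 15): 0.10 × (15 − r) = 1.2, 0.8 and 0.5 points understated for r = 3, 7 and 10.
- The same 10% lost after Visit 2 instead: 0.3, 0.7 and 1.0 points overstated.

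The same amount of loss therefore helps or harms an arm according to when it occurs.

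**Error between arms from loss after Visit 2**, with equal relapse in both arms: (q_A − q_B) × r, in favour of the arm with more such loss.

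| Difference in post-Visit 2 loss | r = 3 | r = 7 | r = 10 |
|---|---|---|---|
| 10 percentage points | 0.3 | 0.7 | 1.0 |
| 20 percentage points | 0.6 | 1.4 | 2.0 |
| 30 percentage points | 0.9 | 2.1 | 3.0 |

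It is zero if r = 0, or if loss and relapse are equal in the arms.

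**Responder count.** Assume normal changes, mean month-3 improvement 15, SD 10 and r = 7. The proportion above 7 points is 0.788 at month 3 and 0.540 at month 6. With 30% versus 10% missing at Visit 3, the false difference is 0.20 × (0.788 − 0.540) = 0.05. Over SD 10 to 15 and r = 3 to 10 it is 1.5 to 7.3 percentage points.

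**False-positive rate.** A simulation used 33 versus 32 patients, no true difference, SD of change 15, values missing at random and a two-sided 5% t-test between arms. With 30% versus 10% post-Visit 2 loss the rate was 6.0% (r = 7) and 7.9% (r = 10). With 50% versus 18% it was 8.3% and 11.8%. With equal loss, or with r = 0, it stayed at about 5%.

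**The case against.** The strongest reply is that the error may be small or absent. The protocol gives no relapse rate; that complete cure is usually not possible does not establish worsening within three months, and lubricants remain allowed. If symptoms hold, carry-forward does no harm of this kind. If loss and relapse are equal, the arm difference is unbiased. Even 3.0 points is under half of the protocol's 7-point threshold, and month-3 comparisons are untouched by later loss. All of this stands, and it limits the size. It does not justify a primary rule that assumes the answer to the month-6 question.

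A reader might infer that whichever arm loses more patients is favoured. The documents do not support that, because loss before Visit 2 is scored as zero change and penalises an arm.

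A reader might also infer that the regimens' differing tolerability makes unequal loss after Visit 2 likely. The drug is taken only up to Visit 2, so tolerability acts mainly before or at that visit. The remaining route is the exit at Visit 2 under section 4.1. If that section governs, those patients are not analysed and carry-forward reaches only adherent patients who miss Visit 3. If section 11.1.2 governs, their Visit 3 value is missing by design; for someone who stopped early, the Visit 2 value is already off drug.

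Finally, 33.8% is inferred, not stated, and comes from a paired calculation on break-up time. Placing all of that loss after Visit 2 is an extreme case.

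**Conclusion.** The point holds for patients seen at Visit 2 and missing at Visit 3. The protocol itself fixes a primary rule that enters a month-3 value as a month-6 off-drug outcome, for the continuous and the responder endpoint alike. A separate analysis plan could add sensitivity analyses, but the primary rule would stand.

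The overstatement within an arm is at most about 1.0 to 3.4 OSDI points, if the whole implied 33.8% loss falls after Visit 2 and relapse is 3 to 10 points. The false arm difference is about 0.3 to 3.0 points if post-Visit 2 loss differs by 10 to 30 percentage points. Relapse, loss by arm and its timing are all assumed. Early loss works in the opposite direction, so the sign of the net error cannot be known in advance. The documents do not show that the final comparison will be biased by any particular amount or toward a particular regimen.

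**What to change.** 1. Reconcile section 4.1 (exits at Visit 2 left out) with section 11.1.2 (intent-to-treat), so that it is clear who is analysed. Changing the missing-data method does not settle this.
2. Replace carry-forward as the primary method. Use a likelihood-based repeated-measures model with baseline, Visit 2 and Visit 3 OSDI all as outcomes and terms for regimen, visit and regimen by visit, or multiple imputation within regimen from baseline and Visit 2. Entering baseline only as a covariate would drop patients with no post-baseline value; either option here keeps them.
3. Derive the count of patients improving by more than 7 points from the same imputation.
4. Add a sensitivity analysis that assumes post-treatment worsening, or non-response, in those missing at Visit 3. This is needed because the methods in step 2 assume data missing at random, which is doubtful for patients who left for adverse events or poor adherence.
5. Keep carry-forward only as a labelled sensitivity analysis.

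The cost is a protocol wording change, a little more analysis work and slightly larger standard errors. No visits, measurements or patients are added.
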